3.3. Approach

3.3.1. Research Design. This research design is illustrated in Fig 5. Aim 1 will use a cross-sectional design to determine baseline relationships between AGE level, intrinsic foot muscle volume, ankle joint mobility, MTPJ movement patterns and MTPJ extension alignment at baseline. Aim 2 is a clinical study with the foot specific intervention focused on improving foot and ankle strength, mobility, and function. The control group will receive a meaningful, comparable, but distinct intervention targeted at improving shoulder mobility, a common limitation in those with DMPN. All participants will repeat testing at 6 months, 1.5 years, and 3 years. Aim 3 will determine the key variables that predict progression of MTPJ extension deformity at 1.5 and 3 years. Intervention status will be entered as a potential predictor variable to examine the ability of a foot specific intervention to impact deformity progression.

Sixty-two participants with DMPN (defined below) and a wide range of MTPJ extension angle will be recruited and followed for 3 years. We will recruit a wide range of MTPJ extension angles to have broad variance in the magnitude and presentation of this deformity so we can understand better the primary factors with which it is associated. We will not break participants into groups based on amount/severity of MTPJ hyperextension allowing us to maintain the continuous nature of important predictors and dependent variables, and hence, increase power of our repeated measures research design.^{55, 56} Only participants with DMPN will

Figure 5: Research Design

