be recruited (vs. otherwise healthy people with MTPJ deformity) so we can focus on the muscle and limited joint mobility problems unique to DMPN. Measures will be taken at baseline, as described below in Table 1, and then all participants will be randomized into a foot specific or a shoulder specific intervention group. Participants will receive 6 intervention visits and a home program. Physical therapist directed interventions will occur during the first 4 months of study participation (3 visits in the first month, and then 1 per month for 3 months). Participants will be instructed, and encouraged by phone call follow up, to continue the home program for the duration of study enrollment. The research coordinator will call participants every 3 months to determine any change in medical status (i.e., skin breakdown, medical emergency), assess adherence with the home program and to keep them “connected” to the study. Participant testing will be repeated at 6 months, 1.5 years, and 3.0 years so that impact of treatment and predictors of change in deformity can be examined. Although we consider this clinical study preliminary, testers will be blinded to group assignment, treatments will take place in a different location than the assessments, and CONSORT guidelines will be followed.

Sample size determination.

Aim 1: A power analysis was conducted based on Hsieh et al's⁵⁷ sample size calculation for logistic and linear regression. 62 participants with DMPN are needed to detect a significant correlation of .44 between the predictor (intrinsic foot muscle volume) and the dependent variable (baseline MTPJ alignment) after adjusting for the other variables (AGE level, maximum ankle dorsiflexion, and maximum MTP extension during ankle dorsiflexion tasks), assuming all the predictors account for 37% of baseline MTPJ alignment. We are confident we will achieve these values for aim 1 since our preliminary data showed a higher correlation ($r=0.60$).

Aim 2: The power analysis for the pilot clinical study is based on a two-sample t-test. We anticipate an effect size of mean ankle joint dorsiflexion range of motion at 6 months, between the foot and shoulder specific intervention groups, of $4 \pm 5^\circ$.⁴⁶ A sample of 52 (26 in each group) will be able to detect this effect size. Our targeted sample size 62 is conservative for this aim considering very low attrition rate at 6 month.

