Aim 3: There is little existing evidence documenting the progression of diabetic foot deformity and we acknowledge that our work proposed in aim 3 is novel and exploratory. Aim 3 Ho3 is powered based on anticipated mean progression of MTPJ alignment 4° every 1.5 years after baseline in 50% people with DMPN assuming a standard deviation of 7.6° with a two-sided paired t-test. We assumed a much more conservative correlation of 0.6 between MTPJ alignment at baseline and 1.5 years later. Our preliminary data documented a progression in midfoot angle deterioration (Meary's angle) that worsened from -15.1 (14.3°) to -22.8 (14.2°) over 2 years in a group of subjects with a history of midfoot deformity, a correlation between measurement time points of 0.81.⁵⁸ Assuming a 20% attrition of the recruited sample, results in a required sample size of 62.

3.3.2. Subject recruitment will occur primarily from the Recruitment Enhancement Core of the Institute of Clinical And Translational Sciences here in the medical center. Several data bases are available to help recruit (e.g., Research Participant Registry through Volunteers for Health, and patient databases of the Applied Biomechanics and Human Biodynamics Laboratories). These resources have sufficient numbers of potential participants to help us achieve our goal. Potential participants will be mailed the consent prior to their first visit to allow them to carefully review the information and formulate questions regarding the study requirements. The requirements, risks and benefits of participation will be explained and all questions the potential participant may have will be answered. If willing to enroll in the study, written informed consent will be obtained. The potential participants will be screened and included if they meet the following inclusion and exclusion criteria:

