Inclusion criteria: Subjects must have Type 2 DM and diabetic PN. The presence of PN will be determined by 1) inability to sense a 5.07 Semmes-Weinstein monofilament on at least one location on the plantar foot, 2) a vibration perception threshold on the plantar great toe greater than 25 V as measured by a biothesiometer, AND 3) an examination score on the Michigan Neuropathy Screening Instrument >2 . As part of the screening process and to ensure a wide range of MTPJ deformity, we will estimate magnitude of MTPJ deformity using a goniometer and our previously published methods⁵⁹ to recruit 1/3 of subjects in each of the following 3 categories of MTPJ severity; $<30^\circ$, $30-50^\circ$, and $>50^\circ$.^{13, 60}

Exclusion criteria: PN with causal factor other than DM (i.e., alcoholic, chemo toxic, lumbar radiculopathy); dialysis; severe arterial disease (ABI < 0.9 or > 1.3)¹; rigid MTPJ deformity; metal implants or pace makers which would interfere with MRI data collection; unable to physically complete testing for the study; lower extremity amputations including multiple toes; acute shoulder pain or disability that would prevent participation in shoulder specific intervention (i.e. severe shoulder pain $>6/10$, rotator cuff tear, upper extremity surgery, thoracic outlet syndrome); pregnant; weight greater than 180 kg (MRI table limitations); presence of a neuropathic ulcer; or age greater than 75 (to minimize extreme age related changes on muscle or joint).

The age exclusion will not be applied for the walking study. Also, MRI compatibility characteristics (e.g., metal implants or pacemakers, pregnant, weight) and shoulder problems will not be applied for the walking study. For the participants in the walking study, people who have neurological disorders (e.g., Parkinson's disease, stroke, multiple sclerosis) that may change walking behavior and use the assistive device when walking will be excluded.

	Time (min)	Baseline (T1)		1- 15 Weeks		6 Month (T2)		7-17 Months		Year 1.5 (T3)		19-35 Months		Year 3 (T4)	
		Visit 1	Visit 2	Visit 1	Visit 2	Visit 1	Visit 2	Visit 1	Visit 2	Visit 1	Visit 2	Visit 1	Visit 2	Visit 1	Visit 2
Informed Consent	15	✓													
Clinical Intake Data	30	✓				✓				✓				✓	
Instrumented Measures															
Skin Fluorescence	10	✓												✓	
Magnetic Resonance	30		✓				✓								✓
Computed Tomography	15		✓				✓				✓				✓
Kinematic Assessment	90	✓				✓				✓				✓	
Clinical Measures															

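### Aim 3 Ho3: the required size of 62 fits a test in about 25 progressors, but the planned paired t-test is not restricted to progressors; its power is about 50-53% if the other half do not change and 98% if 4° is the whole-cohort mean

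*Combined protocol and SAP*

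**What the plan says.** The Aim 3 paragraph under Sample size determination (section 3.3.1), repeated under Sample size in Protection of Human Subjects, bases Ho3 on "anticipated mean progression of MTPJ alignment 4° every 1.5 years after baseline in 50% people with DMPN assuming a standard deviation of 7.6" degrees and a two-sided paired t-test. It adds "We assumed a much more conservative correlation of 0.6 between MTPJ alignment at baseline and 1.5 years later", cites preliminary data on a midfoot angle over 2 years with "a correlation between measurement time points of 0.81", and ends "Assuming a 20% attrition of the recruited sample, results in a required sample size of 62". The same paragraph says "we acknowledge that our work proposed in aim 3 is novel and exploratory".

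Section 3.3.6, Aim 3 Ho3, forms the differences from baseline to 1.5 years and from 1.5 to 3 years, reports their means and SDs, and applies paired t-tests. No subset is named. The proportion who progress by 4° or more within 1.5 years is a separate estimate with a 95% confidence interval. All tests are two-sided at 0.05.

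Three inputs are not given in these paragraphs: the target power, whether 7.6° is the SD at one visit or the SD of the change, and what is expected of the half to whom the 4° does not apply.

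**The concern.** A sample-size statement should describe the test that will be run. Here the effect is attached to half of the participants, while the planned t-test takes the differences without selecting that half. Nor could it sensibly select them: progressors are known only from the outcome. If 62 was reached by sizing a test among progressors and then scaling up, the other participants enter the planned test and can pull the mean change below 4°.

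What is at stake is how an Ho3 result is read. If the test has about even odds of detecting the progression assumed, a non-significant result says little about whether deformity progresses. If 4° is meant as the mean of the whole cohort, the test is well powered and only the justification needs rewording. The text does not tell the reader which applies.

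**Working it through.** **Inputs.** From the Aim 3 sample-size paragraph: 4°, 50%, SD 7.6°, r = 0.6, attrition 20%, N = 62. From section 3.3.6: two-sided 0.05, paired t-test, no restriction to progressors. Assumed, because not stated: 80% target power. Power is from the exact noncentral t distribution.

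**Reproducing 62.**

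- If 7.6° is a per-visit SD, the SD of change is 7.6 × √(2 × (1 − 0.6)) = 6.80°.
- For 4°, n = 24 gives 78.8% power and n = 25 gives 80.6%, so 25 are needed.
- 25 / 0.5 = 50, and 50 / 0.8 = 62.5, against 62 stated (strict rounding up would give 63).

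This route uses every stated input. Two others come close, but each leaves stated inputs out:

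- 7.6° as the SD of change, 80% power: n = 31 (80.9%), and 31 / 0.5 = 62. This uses neither r nor attrition; with attrition it is 77.5.
- 4° in everyone, 7.6° as the SD of change, 95% power: n = 49, and 49 / 0.8 = 61.25. This uses neither r nor the 50%.

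**Power of the planned test.** Completers: 62 × 0.8 = 49.6, taken as 50. If half change by 4° and half by x°, the cohort mean is (4 + x)/2. If the SD applies within each half, the SD of change over the cohort is √(s² + ((4 − x)/2)²), with s = 6.80° or 7.6°; if it already covers the whole cohort, it is s. For x = 0 and s = 6.80°, the first is √(6.80² + 2²) = 7.09°. Each range below runs from the first treatment to the second.

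| Change in the other half | Cohort mean | 7.6° per visit, r = 0.6 | 7.6° as SD of change (r not used) |
|---|---|---|---|
| 0° | 2.0° | 50-53% | 42-45% |
| 1° | 2.5° | 70-72% | 61-63% |
| 2° | 3.0° | 86% | 77-78% |
| 4° (whole cohort) | 4.0° | 98% | 95% |

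Simulating the 0° row with the SD applied within each half gave about 50% and 42%.

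**Change detectable with 80% power, n = 50.**

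- Per-visit SD: cohort mean of 2.75° if the change is uniform, 3.0° if it is confined to half.
- 7.6° as SD of change: 3.1° and 3.4°.

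**Completers needed for 80% power at a 2° mean.** 93 to 101 on the per-visit reading, against about 50 expected.

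**The case against.** The strongest reply is that nothing in the plan says the other half stay still. The low figures depend on that zero: a 1° change in the other half lifts power to about 70%, and 2° to about 86%. There is also a reading on which nothing is wrong with the power. Section 3.3.6 estimates the proportion progressing 4° or more. If the 50% means that half of participants reach 4°, the median change is 4°, and for a roughly symmetric distribution so is the mean, giving 95-98% power. All of this stands. A reader might infer that Ho3 is shown to be underpowered; the documents do not support that, because they leave the behaviour of the other half open. The wording of hypothesis Ho3 itself is not in the text available for review and might define the 50%.

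A reader might also infer that power is 42-53% at the planned correlation. That is not right: at r = 0.6 the no-change figure is 50-53%, and 42-45% arises only if 7.6° is the SD of change, where r plays no part. Nor is 62 an arithmetic error; it follows from the stated inputs to within rounding.

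The preliminary correlation of 0.81 would give 78-84% even with no change in the other half. But it concerns a different angle over 2 years in people with a history of midfoot deformity, and the plan itself chose 0.6.

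Finally, Aim 3 is called exploratory, and Aim 1 separately states that "62 participants with DMPN are needed to detect a significant correlation of .44", so enrolment does not rest on this paragraph. That lowers the weight. It does not make the Ho3 calculation match the Ho3 analysis, since the same paragraph says Ho3 is powered and calls 62 required.

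**Conclusion.** The concern holds as a mismatch between the sample-size statement and the analysis. The only calculation found that uses all the stated inputs gives about 80% power to a test in 25 progressors, and no such test is planned. For the planned test in about 50 completers, the stated inputs are compatible with power from about 50% to 98% on the per-visit reading of 7.6°, and from about 42% to 95% if 7.6° is the SD of change.

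This rests on 80% as the assumed target power in reproducing 62, on reading section 3.3.6 as including everyone with both measurements because it names no subset, and on 20% attrition by the visit concerned. The low end also needs the unstated condition that the other half do not change. It should be fixed, but its weight is modest.

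**What to change.** In both copies of the Aim 3 sample-size paragraph, replace the Ho3 justification with what the all-completer test delivers:

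> Ho3 will be tested in all participants with both measurements. With 62 enrolled and about 50 completers, the paired t-test (two-sided 0.05; per-visit SD 7.6°, r = 0.6, SD of change 6.8°) has 80% power for a cohort mean change of about 2.75° (3.0° if the change is confined to half the cohort), and about 50% power if half progress 4° and half do not change.

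The study statistician should first confirm the target power, the meaning of the 50% and the meaning of 7.6°. If 7.6° is the SD of change, drop the per-visit SD and r from the parenthesis, and use 3.1° (3.4°) and 42-45%. If 4° is the whole-cohort mean, remove the 50% and state 98% power (95% if 7.6° is the SD of change).

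The cost is wording in two duplicate paragraphs. Enrolment, data collection and tests do not change. The one drawback is a less favourable stated figure if only half are expected to progress.

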3.3.4.2. Spiral CT Scanning for MTPJ Deformity and Joint Positions: The purposes of using spiral CT scans for this project are to measure: 1) MTPJ alignment over the 3 year follow up period, 2) measure precisely maximum ankle joint dorsiflexion, and 3) maximum MTPJ active flexion in resting position. CT scans and measurements will be taken in 3 positions. At Visit 4 an additional CT scan will be taken of the foot not followed as part of the study for a comparison.

- 1) Resting position - the calf and foot are placed on a positioning device to standardize ankle position in resting position of 30° plantar flexion (approximate mid position of physiological ankle range of motion from 10° dorsiflexion to 50° plantar flexion, see Fig. 7).^{13, 59} The measure of MTPJ angle in resting position will serve as our primary outcome measure defining the amount of MTPJ hyperextension. MTPJ alignment will be defined as the angle between the phalanx and the extension of the bisector of the metatarsal. A larger angle will indicate less deformity.^{13, 67} (Aims 1-3, Fig. 8).
- 2) Maximum active ankle dorsiflexion - The study participant will be instructed to maximally dorsiflex their ankle joint. Maximum active ankle dorsiflexion and concurrent MTPJ angle will provide the measure of ankle mobility for Aims 1 &2 and an indicator of MTPJ hyperextension movement pattern for Aims 1-3. (Fig. 8b)
- 3) Maximum active MTPJ flexion – The study participant will be instructed to maximally flex their MTPJ with their foot supported in the positioning device. Maximum active MTPJ flexion is an exploratory outcome measure that should improve with the foot specific intervention through increasing MTPJ joint mobility and intrinsic muscle strength. (Fig. 8c)

[figure not shown]

Figure 8. CT positions for measuring MTPJ and ankle angles. MTPJ alignment is the angle between the phalanx and the extension of the bisector of the metatarsal. A larger MTPJ angle indicates less deformity.

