Participants will be positioned supine on the CT scanner table using our previously published reliable and precise methods to measure MTPJ angles.^{54, 59, 67-69} Briefly, we use a multi-slice Siemens Sensation 64 CT scanner (Siemens Medical Systems, Inc., Iselin, NJ) that allows a spatial isotropic resolution of 0.6 millimeters (mm) for a clear detailed visualization with a rapid acquisition time (gantry rotation speed of 0.5 seconds). The following CT parameters will be used to acquire the scans: 0.5 second rotation time, 64×0.6 mm collimation, 220 mAs, 120 kVp, a pitch of one, and a 512×512 matrix. The lower one third of the leg and the entire foot are scanned. Acquisition time will depend slightly on the size of the subject's foot but generally is less than 2 minutes of x-ray tube time for all 3 scanning positions. The CT projection data sets will be reconstructed with a resolution of approximately $0.6 \times 0.6 \times 0.6$ mm³. The CT data will be de-identified, archived on DVDs using DICOM format, and processed in the Electronic Radiology Laboratory. The SCT data will be converted from DICOM format to an Analyze software file format⁵⁴ (ANALYZE Software, Biomedical Resource Mayo Clinic, Rochester, MN). As illustrated in Figure 8, the following angles will be measured for all three scans: (1) MTPJ angle: 180° minus the angle between the phalanx and metatarsal for all five metatarsals and (2) Ankle joint position: tibia and a line drawn between the bottom of the calcaneus and the second metatarsal head.⁵⁴

Preliminary Data: We recruited 19 participants with DMPN (mean age 59 ± 9 years) who met the identical inclusion and exclusion criteria proposed in this project. MTPJ alignment in resting will be reported in combination with the intrinsic muscle volumes in section 3.3.4.3, Fig 9. During the maximum active ankle joint dorsiflexion task, MTPJ angle was negatively correlated with maximum ankle joint dorsiflexion (Spearman's rho $r = -.58$, $p < .01$). This finding supports the hypothesis that the MTPJ deformity is

associated with limited ankle joint mobility. This proposal will examine the role of limited ankle joint mobility in MTPJ deformity development and progression and the ability of a foot specific intervention to improve ankle dorsiflexion range of motion.

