Preliminary data: Intrinsic foot muscle and fat volumes were measured from the talonavicular joint through 50% of the 2nd metatarsal in the 19 participants with DMPN described above. The average muscle volume was $64.5 \pm 24.6 \text{ cm}^3$ and total fat volume was $32.7 \pm 15.5 \text{ cm}^3$. Less MTPJ deformity (greater MTPJ angle) was positively correlated with greater total muscle volume ($r = .60, p < .01$, Fig. 9). Total fat volume was not significantly associated with MTPJ angle ($r = -.32, p = .18$) in this preliminary investigation. These data support the hypothesis that a decline in intrinsic muscle volume is associated with MTPJ deformity but does not completely explain the magnitude of the deformity. This proposal will expand on our preliminary work by recruiting a larger sample, following participants over 3 years, examining the contribution of multiple potential contributors (AGE level, MTPJ hyperextension movement pattern, and limited ankle joint mobility) to MTPJ alignment, and exploring the ability of a foot specific intervention to de-couple diabetes related mechanisms from MTPJ deformity.

[figure not shown]

Figure 9. Better MTPJ alignment (increasing values) is correlated with greater intrinsic muscle volume.

3.3.4.4. Foot and ankle motion function using 3D motion analysis: The primary purpose of 3D motion analysis is to measure the MTPJ hyperextension movement pattern observed during dorsiflexion tasks. During our pilot work for this proposal we had 19 participants, described above, complete numerous movement tasks thought to elicit the MTPJ hyperextension movement pattern including: sit-to-stand, walking at a self-selected speed, ankle dorsiflexion and toe flexion tasks with the knee flexed and extended, and a sitting foot arch elevation task. The sit-to-stand and knee extension ankle dorsiflexion tasks were the most capable of clearly differentiating those with the greatest deformity from those with the least deformity and will be included in this proposal. In addition, our previous work indicates that measuring forefoot plantarflexion motion relative to the hindfoot during a single leg heel rise task is a foot specific challenge capable of identifying those with poor foot intrinsic foot muscle quality in those with DMPN and so this task will also be included.⁵³ (Aims 1-3)

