Sit-to/from-stand task: MTPJ extension excursion during sit-to/from-stand was significantly correlated with MTPJ alignment ($r=.48$, $p<.02$) in our 19 pilot participants. To visualize the difference in the movement pattern we graphed the excursion of the 2nd MTPJ during the task for the 5 participants with the largest MTPJ deformity (red) and the 5 participants with the smallest MTPJ deformity (blue). Those with MTPJ deformity had greater MTPJ extension excursion during the sit-to/from-stand components of the task when compared to those without MTPJ deformity. (Fig. 10) These preliminary data provide support for our hypothesis that those with MTPJ deformity have the MTPJ hyperextension movement pattern repeated during daily tasks and our proposal will examine the relationship between this pattern and the progression of MTPJ deformity.

Ankle Plantarflexion/Dorsiflexion Task: Ankle and MTPJ motion was measured during active ankle plantarflexion and dorsiflexion in our pilot participants. Maximum ankle dorsiflexion was significantly correlated with MTPJ alignment ($r=.40$, $p=04$), where those with deformity showed greater deficits in dorsiflexion. To visualize the difference in the movement pattern, we graphed ankle motion versus simultaneous MTPJ motion (Fig. 11) for the entire task for the 5 participants with the largest MTPJ deformity (red) and the 5 participants with the smallest MTPJ deformity (blue). Those with MTPJ deformity showed deficits in dorsiflexion (positive, x-axis), and extended the MTPJ over a greater range than those without deformity (positive y-axis, ~30 deg vs. ~20 deg). Those with deformity also showed a steeper rise in MTPJ extension as the ankle moved into dorsiflexion (lower bound of motion curve).

[figure not shown]

Figure 10: Second MTPJ Extension Excursion during sit-to/from-Stand. The DMPN with MTPJ deformity (red) have more MTPJ extension in both sit-to/from stand compared to DMPN without MTPJ deformity (blue).

[figure not shown]

Figure 11. MTPJ angle during ankle plantarflexion and dorsiflexion. Starting at 0° ankle plantarflexion/dorsiflexion, the motion curve moves counter-clockwise as the ankle plantarflexes then dorsiflexes. The DMPN with MTPJ deformity (red) have more MTPJ motion and a steeper increase in MTPJ extension as the ankle moves into dorsiflexion (lower bound of curve).

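### Does the primary-outcome MTPJ angle run in the opposite direction to the one the plan states?

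*Combined protocol and SAP*

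**What the plan says.** Section 3.3.4.2 of the combined protocol and SAP makes the resting CT angle the "primary outcome measure defining the amount of MTPJ hyperextension". It gives the geometry in words: "MTPJ alignment will be defined as the angle between the phalanx and the extension of the bisector of the metatarsal". The direction follows: "A larger angle will indicate less deformity". Later in the same section, for all three scan positions (rest, maximum active dorsiflexion, maximum active MTPJ flexion), the measurement is "MTPJ angle: 180° minus the angle between the phalanx and metatarsal for all five metatarsals", with a reference to Figure 8.

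The direction is repeated in the Figure 8 caption, in the preliminary data of section 3.3.4.3 ("Less MTPJ deformity (greater MTPJ angle) was positively correlated with greater total muscle volume") and in the Figure 9 caption, which equates rising values with better alignment.

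Section 3.3.6 defines Aim 3 progression as the earlier value minus the later one. For Ho3 it also estimates the proportion progressing by at least 4° within 1.5 years, with a 95% confidence interval. That section calls the differenced variable MTPJ deformity; it does not call it angle or alignment.

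**The concern.** The deformity is hyperextension. An angle between the phalanx and the forward line of the metatarsal, with no side or sign, gets bigger as the toe extends. So does 180° minus the ordinary included angle. The sentence on direction says the reverse, and the visible text never says that extension counts as negative or on which side of the joint the angle is taken.

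Two pilot results in section 3.3.4.4 add to the doubt. One reads "MTPJ extension excursion during sit-to/from-stand was significantly correlated with MTPJ alignment ($r=.48$, $p<.02$) in our 19 pilot participants", and the text goes on: "Those with MTPJ deformity had greater MTPJ extension excursion during the sit-to/from-stand components of the task". Taken at face value, higher alignment values go with deformity. The other reads "Maximum ankle dorsiflexion was significantly correlated with MTPJ alignment ($r=.40$, $p=04$), where those with deformity showed greater deficits in dorsiflexion", which implies the opposite.

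At stake are the sign of every Aim 1–3 estimate for the primary outcome and the Ho3 proportion. If the data were scored on an unsigned scale, or if the variable in section 3.3.6 were taken as severity, baseline minus follow-up would be negative for a foot that worsened. The 4° rule would then count the feet that improved.

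**Working it through.** **1. The plan's own figure, and whether direction affects it.** Inputs from the Aim 3 sample-size paragraph in section 3.3.1: change 4°, SD 7.6°, correlation 0.6, two-sided paired t-test, progression in 50% of people, 20% attrition. Alpha of 0.05 is from section 3.3.6. Power is not stated, so 80% is assumed.

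- SD of change = 7.6 × √(2 × (1 − 0.6)) = 6.80°.
- Paired t-test for 4° at 80% power: 25 pairs (power 0.806).
- 25 / 0.5 = 50, and 50 / (1 − 0.20) = 62.5, against the stated 62.

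Reversing the sign of the angle turns 4° into −4°. A two-sided test gives the same n and the same p-value.

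**2. Geometry of the two definitions.** Extension is taken as 0°, 30° and 50°, and flexion as 20°.

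| Reading | 20° flexion | Straight | 30° extension | 50° extension |
|---|---|---|---|---|
| Angle to the metatarsal's forward line, unsigned | 20 | 0 | 30 | 50 |
| 180° minus the ordinary included angle | 20 | 0 | 30 | 50 |
| 180° minus the plantar-side angle | 20 | 0 | −30 | −50 |

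Three things follow. Both definitions place zero at a toe in line with its metatarsal, so the zero point is fixed. On the unsigned rows, 20° of flexion and 20° of extension would score the same, which cannot work for the maximum-flexion scan. On the plantar-side row, larger means less extension, as the plan states.

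**3. The progression rule on the stated direction.** Suppose a toe goes from 30° to 34° of extension. On the signed scale, baseline minus follow-up = −30 − (−34) = +4°, and the toe is counted as a progressor. That is correct. On an unsigned scale, 30 − 34 = −4°, and it is missed.

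The Aim 3 sample-size paragraph already uses a signed foot angle in which lower is worse: Meary's angle went from −15.1 to −22.8. Baseline minus follow-up there is −15.1 + 22.8 = +7.7°, positive for worsening, the same orientation as section 3.3.6.

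**4. Size of the error if the direction were ignored.** This is an illustration that assumes normally distributed changes. If half worsen by a mean of 4° and half do not change on average, with SD 6.80°:

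- P(worsen by ≥4°) = 0.5 × P(Z > 0) + 0.5 × P(Z > 4/6.80) = 38.9%.
- P(improve by ≥4°) = 0.5 × P(Z > 8/6.80) + 0.5 × P(Z > 4/6.80) = 19.9%.

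If all worsen by a mean of 4°, the figures are 50.0% and 12.0%. With 7.6° taken as the SD of change, they are 40.0% and 22.3%, or 50.0% and 14.6%. The rule would report the second figure of each pair only if the angle were scored against the stated direction.

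**5. The pilot correlations.** On the stated direction, r = .40 with dorsiflexion has the expected sign, and r = .48 with extension excursion does not, if excursion is scored with extension positive. The text does not give that scoring for the sit-to-stand task. The axis signs described for Figure 11 belong to a different task, and Figure 10 is not visible. With n = 19 the 95% interval for r = .48 is 0.03 to 0.77. A dropped minus sign or a differently signed excursion would explain it. Neither correlation sets a rule for scoring or analysis.

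**The case for a change.** The strongest case for a change is that a primary outcome and its 4° threshold should be reproducible from the written plan alone. The visible text does not make the reader choose the signed angle. The resting angle is described as the amount of hyperextension, the goniometer screening categories in section 3.3.2 rise in positive degrees with severity, and section 3.3.6 calls the differenced variable deformity, which in ordinary use means severity. A reversal would leave two-sided p-values unchanged, so the p-values would not reveal it. The remedy would be wording only.

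Part of this stands. The visible text does not put a sign on extension, the label in section 3.3.6 is loose, and the printed sign of r = .48 does not sit easily with the stated direction.

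The rest does not carry. The goniometer categories are a recruitment screen and not the CT outcome. The direction is stated four times and never contradicted as a rule. A drawn angle in Figure 8 is where side and sign would normally appear, and its absence from the extracted text is not a gap in the plan. To get the wrong proportion, an analyst would have to score the angle unsigned, disregard the repeated statements that larger is better, overlook that flexion and extension would then be indistinguishable, and still apply a subtraction that works only on the other scale.

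**Conclusion.** The concern does not call for a change. What is missing is a written sign convention, and the rest of the plan leads an analyst to only one workable choice: straight toe at 0°, extension negative, larger meaning less deformity. On that choice both definitions, the four statements of direction and the baseline-minus-follow-up rule agree, and the error is zero. The contrast of about 12–22% with about 39–50% describes a mistake the plan's own words rule out. It also rests on assumed normal changes and assumed mixtures of worsening and stable feet. N = 62, power and two-sided p-values do not depend on the sign.

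The label in section 3.3.6 and the sign of r = .48 are clerical matters. Tidying them would alter no estimate, test or sample size. This conclusion takes the stated direction as the intended one. Figure 8 could not be checked, but it is cited as the illustration of these angles, and its caption repeats that direction.
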